Longitudinal Study of Dental Implant Therapy in HIV Positive Patients

Study Protocol & Statistical Analysis Plan

NCT01211288

August 30, 2019

[name], DMD, Principal Investigator
University of Alabama at Birmingham
[name]

APPENDIX 1

Protocol

D-2007-51

PROTOCOL SYNOPSIS

Title

Longitudinal Study of Dental Implant Therapy in HIV Positive Patients

Investigator (*Insert here the name, mailing address, email address, and phone number of the Co-ordinating Investigator (for multi-centre studies) or the Principal Investigator (for single-centre studies)*)

A. Principle Investigator:

[name], MS, DMD, FAGD, FACD
Prosthodontist, Associate Professor, UAB Comprehensive Dentistry Department
[name]
[name]
[contact]
[contact]

B. Co- Investigators:

1. [name], DMD
General Dentist, Assistant professor, Director 1917 HIV/AIDS Dental Clinic, UAB Comprehensive Dentistry Department
2. [name], DMD, FAGD, MAGD
Assistant clinic professor, UAB Comprehensive Dentistry Department
Private Practice General Dentistry, Wedowee AL.
3. [name] - [name], MS, DMD
Prosthodontist, Professor and Chair, UAB Comprehensive Dentistry Department
4. [name], DMD, PHD
Prosthodontist, Associate Professor, UAB Comprehensive Dentistry Department
5. [name], DMD
Radiologist, Associate Professor, Director of Clinical Operations and Dental Radiology, UAB Diagnostic Science Department
6. [name], MS
Oral and Maxillofacial Pathologist, Assistant Professor, UAB Anatomic Pathology Department

<>>

Study centre(s) and number of subjects planned (*Insert here the address where the study will be conducted, number of patients planned and if applicable distribution of patients per site*)

1. UAB School of Dentistry
Department of Comprehensive Dentistry
[name]
[name]

Total 40 patients will be treated in the 2nd floor main clinic
 20 HIV (+) patients will be selected from the 1917 Dental Clinic and 20 patients will be selected from UAB School of Dentistry patients.

2. Cone Beam CT scanned at UAB School of Dentistry Periodontal research clinic

<>>

Study period

<<Month and year>>

<<Month and year>>

Estimated Start date and End date

January 2010

December 2014

Date of first data available for presentation

December 2011

Objectives (Insert objectives)

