1. To study the short term and long term osseous integration of implant supported restorations on immunocompromised (HIV positive) patients.
2. Radiographic examination of implant osseous integration using Cone Beam CT and traditional vertical bitewing radiographs.
3. Histologic examination of bone biopsies from each implant surgical site, at the time of initial placement, and from failing implant sites, including histologic examination of the implant-bone interface.

Study design (Insert a one-sentence summary of study design features)

Provide HIV (+) patients with implant supported restorations, using HIV (-) patients as controls.

<>>

Target patient population (Insert a description of target population and indication studied)

20 HIV (+) patients with the following requirements:

Age 19 and older,

Hemoglobin >8g/dl , Absolute neutrophil count >750/mm³, Platelet count >75,000cells/mm³, AST < 5 times the upper limit of normal (ULN),

Bilirubin < 2.5 times ULN, Alkaline phosphate < 5 times ULN, Creatinine < 2.5 mg/ml

Non- smoker (quite smoking at least 6 months)

Controlled Type II diabetes

Controlled hypertension

Non bisphosphate user

Non- bruxer

Misch Available Bone classification divisions A, B, C

Misch Bone Density classification D1, D2, D3

Minimal available bone width 5mm

Minimal available bone height 10mm

Minimum bone graft with freeze dried demineralised bone upon implant placement

Extraction site has to be healed up for minimum 3 months for mandibular and 6 months for maxillary before implant placement

Flap or flapless implant placement with surgical stent as guidance

Implant supported restorations are limited to the following edentulous areas:

Mandibular arches, excluding 3rd molar areas

Maxillary anterior and premolar areas

Exclude extensive bone graft involvement and sinus lift

No immediate implant loading

Total numbers of implant restorations are limited to;

Maximum of 4 units of fixed prosthesis with minimum 2 implants support for maxillary and mandibular anterior region,
 3 units bridge with 2 implant supports,
 2 units bridge with 2 implant supports,
 Single implant support crown

Permanent implant restoration 3 months after implant placement for mandibular and 6 months for maxillary.

All implant supported restorations will be cement-retained restorations.

Dental material: either full metal restoration or porcelain fused with metal restoration.

20 HIV-negative patients following the same requirements as above.

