The primary variable examined will be the treatment outcome as measured according to the Albrektsson and Zarb criteria for implant success. Patients will be examined at each interval for the presence of pain, infection, mobility, and radiographic bone height of each implant

Additional clinical assessments (*Describe use of any additional clinical assessments e.g. clinical photographs etc.*)

1. All selected patients will have prior medical authorization to have surgical procedure performed. Patients will undergo complete oral clinical examination as well as cone beam CT scan, selected periapical and vertical bitewing radiographs on planning implant placement site, full mouth photography, diagnostic casts, and surgical stent before implant placement.
2. Cone Beam CT on the implant sites of arches at 1 year, 2 years and 3 years post placement follow-up (Cone Beam CT provides 1:1 ratio image, view in 3- dimensions, limited radiation exposure). The images will be evaluated by the dental radiologist.
Compare accuracy and efficiency of Cone Beam CT image of alveolar bone around implant in 3-dimensions vs. of conventional standard X-ray examination of bone lost around implant in 2-dimensions.
3. Histologic examination of the bone biopsy from the implant sites will provide scientific evidence of the bone changes that may occur in the process of implant osteointegration under immunocompromised conditions.
4. Photograph during implant restoration procedure and after complete restoration.
5. Patient post-implant restoration survey (such as: general satisfaction, social life, mastication on hard food, comfort).

Statistical methods (*Describe as relevant the statistical methods to be used, the populations to be analysed (e.g. intention to treat, per-protocol), and any interim analyses*)

Descriptive statistics will be applied to acquire the mean parameter values, range, and implant success rate as determined by the Albrektsson and Zarb criteria.

With rigorous inclusion/exclusion criteria proposed, parametric data will be analysed using ANOVA methods. Nonparametric (yes/no) criteria will be analyzed with the Chi-Square method.

Publications / Presentations (*Describe your plans with regard to publications or public presentations i.e. what journals or conferences/meetings*)

Peer reviewed journals such as: Journal of American Dental Association, Journal of Prosthodontics, Journal of General Dentistry.

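### The patient survey has no pre-treatment counterpart, so change in social life, chewing and comfort is not measured, and any comparison of the HIV groups on it would mix starting level with response

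*Combined protocol and SAP*

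**What the plan says.** The survey appears once, as the last of five items under Additional clinical assessments: "Patient post-implant restoration survey (such as: general satisfaction, social life, mastication on hard food, comfort". The item places it after restoration. It names no instrument, scale or visit.

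Item 1 of the same section lists the work-up before placement: "Patients will undergo complete oral clinical examination as well as cone beam CT scan, selected periapical and vertical bitewing radiographs on planning implant placement site", followed by photography, casts and a stent. No questionnaire is in that list, and none is mentioned elsewhere.

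The Study design entry reads "Provide HIV (+) patients with implant supported restorations, using HIV (-) patients as controls". The groups come from different sources: "20 HIV (+) patients will be selected from the 1917 Dental Clinic and 20 patients will be selected from UAB School of Dentistry patients". Under Target patient population the controls are "20 HIV-negative patients following the same requirements as above"; those requirements cover age, laboratory values, habits, medical conditions, bone, and the site and type of restoration.

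The Statistical methods section gives one general plan besides descriptive statistics: "With rigorous inclusion/exclusion criteria proposed, parametric data will be analysed using ANOVA methods", and "Nonparametric (yes/no) criteria will be analyzed with the Chi-Square method". It names no baseline covariate, change score or matching. The three objectives concern osseous integration, radiographic examination and histology, and the primary variable is implant success by the Albrektsson and Zarb criteria.

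**The concern.** Social life, chewing hard food and comfort all have a level before treatment. That level may differ between patients of an HIV clinic and general dental-school patients. It may also differ with the extent of tooth loss, since the permitted restorations run from a single crown to four units. No entry criterion equalises these things.

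Two consequences follow from asking only afterwards. First, a post-treatment score says where a patient ended, not how far he or she moved. Second, if the groups are compared on that score, a lower social-life score in HIV-positive patients could be read as a poorer result of treatment when it was there at the start. Once a patient has been treated, an answer given at the time before treatment can no longer be obtained; only recall remains.

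**Working it through.** **Reading check.** The whole document was read for a pre-treatment survey, a matched control selection or a baseline adjustment. There is none. There is also no stated alpha, power, SD or sample-size calculation, so the plan has no figure to reproduce. What follows is an illustration.

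**Inputs.** From the documents: 20 patients per group, not randomised, both groups treated. Assumed: a scored item with SD 1 in each group before and after treatment; two-sided 5%; no effect of HIV status on response to treatment; a starting gap *g* between groups, in SD units; a within-group pre/post correlation *r*.

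**Precision.** SE of a difference in post-treatment means = √(2/20) = 0.316 SD. The difference detectable with 80% power is (1.960 + 0.842) × 0.316 = 0.89 SD.

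**Post-only comparison, full carry-over.** If both groups gain equally, the whole gap remains. At *g* = 0.5 the noncentrality is 0.5/0.316 = 1.58, and the t test on 38 df rejects in about 34% of trials.

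**Post-only comparison, partial carry-over.** If the post score depends on HIV group only through the baseline score, the remaining gap is *r* × *g*. For *g* = 0.5:

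| *r* | remaining gap (SD) | noncentrality | rejects |
|---|---|---|---|
| 0.3 | 0.15 | 0.47 | 7.5% |
| 0.5 | 0.25 | 0.79 | 12% |
| 0.7 | 0.35 | 1.11 | 19% |

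A simulation of 10,000 runs per setting agrees. Over the same range of *r* it gives about 6% to 10% for *g* = 0.3 and 11% to 40% for *g* = 0.8. ANCOVA on the baseline score stays between about 4.5% and 5.5% in every setting of this model.

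**Does comparing change solve it?** Only under equal gains. Under partial carry-over the group difference in change is *r* × *g* − *g*, so its bias has size (1 − *r*) × *g* in the opposite direction, with SE √(2(1 − *r*)) × √(2/20). For *g* = 0.5:

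| *r* | bias of change (SD) | SE | rejects |
|---|---|---|---|
| 0.3 | 0.35 | 0.374 | 15% |
| 0.5 | 0.25 | 0.316 | 12% |
| 0.7 | 0.15 | 0.245 | 9% |

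At *r* = 0.3 the change score is more biased than the post-only score (0.35 against 0.15 SD), at 0.5 equally biased, and at 0.7 less.

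**Does ANCOVA always solve it?** No. Under equal gains the post gap is *g* and the within-group slope is *r*, so ANCOVA leaves *g* − *r* × *g* = (1 − *r*) × *g*, while the change score is unbiased. The two analyses rest on different assumptions about how the starting gap evolves, and in non-randomised groups the data at hand do not settle which is right. Both need the baseline that the plan does not collect.

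**The case against.** The strongest reply is that the documents never plan the inference at risk. The survey is neither an objective nor the primary variable. It has no hypothesis and no analysis of its own, and a comparison of HIV groups on it is inferred from the controlled design and the general ANOVA and chi-square text. As a description of how patients regard a finished restoration, a post-treatment survey is legitimate, and satisfaction with that restoration has no true baseline. The document is a synopsis, and the survey items are given only as examples. Nothing excludes questions that ask patients to compare with before treatment, although those carry recall bias. Finally, every number in the illustration is assumed.

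Most of this stands, and it limits the point. A reader might infer that the plan will report pre-existing group differences as treatment results; the documents do not say so. A reader might also infer that a baseline survey would show what implants achieved. It would not: both groups receive implants and no group is untreated, so it would show change, not its cause. And the 34% should not be quoted alone, because it needs the whole starting gap to persist.

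What the reply does not remove is the gap itself. Three of the four named items have a pre-treatment level, the plan does not record it, and the only analyses named make no adjustment.

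**Conclusion.** The point holds in a limited form. As written, the plan does not measure within-patient change in social life, chewing or comfort, and a group comparison of the survey, if made, could not separate starting level from response to treatment. For an assumed starting gap of 0.5 SD, the false-positive rate of a post-only test at a nominal 5% is about 8% to 19% under partial carry-over and about 34% under full carry-over. That there is inflation depends only on some of a real starting gap persisting; its size depends on inputs the documents do not give. The primary implant-success outcome and the three stated objectives are not touched. This is a cheap improvement to an additional assessment, not a flaw in the main conclusion.

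**What to change.** 1. Add the items that apply before treatment (social life, chewing hard food, comfort, satisfaction with the current dentition) to the pre-placement examination in item 1. Repeat the same items at one fixed time after restoration, and state the instrument, scale and visit.
2. In Statistical methods, state that within-patient change is reported descriptively in each group. Compare groups on the post-treatment score adjusted for the baseline score (ANCOVA), with the comparison of change scores as a sensitivity analysis. Say that the two rest on different assumptions in non-randomised groups, and that a result on which they disagree is not firm.
3. Report satisfaction with the finished restoration as post-treatment description only.
4. Do not credit change wholly to implants, since no group is untreated.
5. Where the baseline can no longer be collected, report the survey as descriptive post-treatment status, with no claim of improvement or of an HIV effect.

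The cost is one short questionnaire at a visit that already takes place, a few minutes for each of 40 patients. No treatment or clinical procedure changes.

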Investigational product/comparator (*State the devices / products that will be investigated // used and for comparative studies also the comparator/s*)

1. Cone beam CT full facial scan on every patient before and after implant placement on surgical site single arch at 1 year, 2 year, 3 year follow up (i-CAT \$600 per patient x40 = \$ 24,000)
2. Facilitate Pro software convert Dicom images for implant placement design and surgical stent fabrication (\$12,000)
3. Surgical tools for implant placement:
 (syringe, needles, elevators, periotomes, extraction forceps #150 & #151, bone spreading chisels, bone grinder, bone trap, bone compactor, bone curette, osteotomes, resorbable and non-resorbable sutures, needle holders, scissors
 Surgical stent, two surgical bundles, two surgical trays, one surgical motor, two surgical handpiece heads, two full restorative trays and bundles, surgical saline bags for surgical irrigation, disposable irrigation kits for drill unit, disposable drills. Pulse oximetry) (\$ 30,000)
4. Root form implants of various sizes, cover screws (\$250 per implant x est. 80 = \$ 20,000)
5. Freeze dried demineralised bone as bone graft material (\$ 100/ 0.5cc vial x est.20 = \$ 2,000)
6. Resorbable membrane (\$ 100/ membrane x est. 20 = \$ 2,000)
7. Poly vinyl siloxane impression materials (\$ 4,000)
8. Prosthodontic instrument kits plus laboratory fee (impression transfer material, implant abutments, implant analogues, Cresco Precision system)
 (\$ 400 per implant restoration x est. 80 = \$32,000)
9. Two WhipMix Semi- adjustable articulators (\$ 800 x 2 = \$1,600)
10. Half-time patient coordinator (\$ 18,000 or neg.)
- *11. Computer for information storage and portable printer (\$ 3,000)
12. SLR camera with Macro-lens and flash (\$ 2,500)
13. Histological examination of 40 bone biopsies processed at UAB Anatomic Pathology Lab, including special stains and decalcification (\$ 8,000)
14. Processing of failed implants at the UAB Bone Core facility with subsequent histologic examination of implant-bone interface (\$200.00 per failed implant x est. 5 = \$1,000)
15. Journal publication expenses (\$2000.00)
16. Travel expenses to national and/or international meetings by the PI investigator and one co-investigator (\$ 4000.00)

Total budget: \$166,000

Outcome variables (Indicate which variable is the primary variable for the study)

Efficacy (*List all efficacy variables and indicate clearly your primary outcome variable*)

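### Implant success is a crude rate tested by chi-square, with no time horizon and no use of partial follow-up, while the calendar assures year-3 data only for implants placed by about December 2011

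*Combined protocol and SAP*

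**What the plan says.** The Efficacy entry makes the primary variable implant success by a cited published set of criteria, checked at intervals that it does not define. The Statistical methods section gives the whole analysis. It opens: "Descriptive statistics will be applied to acquire the mean parameter values, range, and implant success rate". It then assigns ANOVA to parametric data and chi-square to yes/no criteria. It names no time point for the rate, no denominator, no analysis population and no rule for implants whose follow-up is incomplete.

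Item 2 of Additional clinical assessments sets the imaging schedule: "Cone Beam CT on the implant sites of arches at 1 year, 2 years and 3 years post placement follow-up". The Study period entry gives "Estimated Start date and End date" as January 2010 and "December 2014", and sets "Date of first data available for presentation" at December 2011. No section gives an enrolment window or a last placement date.

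On size and source: "Total 40 patients will be treated in the 2nd floor main clinic", and "20 HIV (+) patients will be selected from the 1917 Dental Clinic and 20 patients will be selected from UAB School of Dentistry patients". The budget list costs implants at a unit price "per implant x est. 80" and allows for 5 failed implants.

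**The concern.** The study is titled longitudinal, and its first objective covers both short-term and long-term integration. A success rate without a horizon does not say which of these it measures. A crude proportion also needs one yes or no per implant. An implant followed for 2 of the 3 years, whether placed late or lost, does not supply that for year 3, so someone must decide whether to count it as a success, leave it out, or keep it only if it failed. The plan does not decide, so the choice could be made after the data are seen. With about 5 failures budgeted, moving one or two implants between categories changes the headline result.

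**Working it through.** The plan states no success rate by time, no power and no sample-size calculation, so there is no figure of its own to reproduce. The check has two parts: the calendar, which is arithmetic on stated dates, and an illustration, which rests on assumptions.

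**Calendar.** Count months from the start of January 2010; the end of December 2011 is month 24 and the end of December 2014 is month 60.

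- Latest placement for a year-3 visit by study end: 60 − 36 = month 24, about December 2011.
- Latest placement for a year-1 visit by December 2011: 24 − 12 = month 12, about December 2010.
- With even placement, the share able to reach year 3 is 100% for a window of 24 months or less, 24/36 = 67% for 36 months, and 24/48 = 50% for 48 months.

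**Illustration: inputs.** True 3-year failure F = 5/80 = 6.25%. Both counts come from the budget list; using them as a 3-year risk is an assumption. Constant hazard, failures found only at annual visits, and even placement are also assumptions.

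- Hazard: −ln(1 − 0.0625)/3 = 0.0215 per year.
- Failure by year k is 1 − 0.9375^(k/3): 2.13% at year 1, 4.21% at year 2, 6.25% at year 3.

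**Study end, placement over 36 months.** Two-thirds of implants reach year 3; the last third reach only year 2.

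- Unseen counted as successes: (2/3)(6.25%) + (1/3)(4.21%) = 5.57%.
- Unfailed unseen implants dropped, their early failures kept: 5.57/(5.57 + (2/3)(93.75)) = 5.57/68.07 = 8.2%.
- Only implants due at year 3 used: 6.25%, with a third of the implants discarded.

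**Study end, placement over 48 months.** Half reach year 3, a quarter reach year 2 and a quarter reach year 1.

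- Unseen counted as successes: 0.5(6.25%) + 0.25(4.21%) + 0.25(2.13%) = 4.7%.
- Unfailed unseen dropped: 4.71/(4.71 + 0.5 × 93.75) = 4.71/51.58 = 9.1%.

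| Placement window | Unseen = success | Unfailed unseen dropped | Only those due at year 3 |
|---|---|---|---|
| 24 months or less | 6.25% | 6.25% | 6.25% |
| 36 months | 5.6% | 8.2% | 6.25% |
| 48 months | 4.7% | 9.1% | 6.25% |

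**Sensitivity.** If failures are found as they occur rather than at annual visits, the 36-month figures become 5.91% and 8.64%. With an assumed 3-year failure of 20% and annual detection, they become 17.9% and 25.2%.

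**December 2011, placement over 24 months.** Half the implants have had a year-1 visit. Counting the rest as successes gives 0.5 × 2.13% = 1.1% against a true 2.1%. Leaving them out gives 2.1%.

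**Loss to follow-up.** This can occur whatever the placement window. If 20% of a group is lost after year 1 (assumed), counting them as successes gives 0.8(6.25%) + 0.2(2.13%) = 5.4%. Dropping only the unfailed ones gives 5.43/(5.43 + 0.8 × 93.75) = 6.7%.

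**Life table on the same 36-month case.** Each year's conditional risk is 2.13% among implants still followed, so cumulative success is 0.9787³ = 93.75%. This recovers the assumed 6.25% failure and uses the late implants up to year 2.

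**The case against.** The strongest reply is that the calendar works. A five-year study with three years of follow-up leaves two years to place implants in 40 patients, and if that is met, late placement causes no distortion at the end. This stands: unequal follow-up at year 3 is possible but not inevitable, and the dates are only estimates. It does not deal with loss to follow-up, and nothing in the plan ties placement to month 24.

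A reader might infer that implants not yet seen will count as successes, so that success is overstated at every data cut. The documents do not say this. Patients are to be examined at each interval, and a rate among those examined is at least as natural a reading. The direction depends on the unwritten rule, as the table shows.

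A reader might also infer that HIV-positive patients will be made to look better than they are, because they come from a different clinic. No later placement or greater loss in that group is documented, and all 40 patients are treated in the same clinic.

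December 2011 is labelled only as the date of first data for presentation. No success comparison is assigned to it, so the point applies there only if a year-1 success figure is shown.

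Finally, the effect is small in implants: 5.57% of 80 is 4.5 failures against 5.0. Annual detection also widens the gap, since restoration at 3 or 6 months offers an earlier contact. Both points are fair. Small numbers limit the group test more: with 40 implants per group treated as independent, power for an assumed 6.25% against 12.5% is about 16%. That is a separate weakness and does not define the rate.

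**Conclusion.** The point holds as a weakness in the method and its specification, not as a demonstrated upward bias. The primary outcome is analysed by a crude rate and chi-square that have no time horizon and cannot use partial follow-up, in a study with visits to 3 years and no last placement date.

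If placement runs to 36 months, the same data could be reported as 5.6% or 8.2% failure when the assumed truth is 6.25%. This rests on constant hazard, annual detection and even placement, none of which is in the documents. If all placement ends within 24 months, late placement adds nothing and only loss to follow-up remains. The change should be made because it is cheap and standard, and it removes a choice that could otherwise be made after the data are seen.

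**What to change.** In Statistical methods:

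- Report cumulative implant success by life table or Kaplan-Meier at years 1, 2 and 3 for each HIV group, with numbers at risk. Censor at the last visit attended. Keep the plan's own success criteria as the definition of failure.
- Compare the groups with a method that respects several implants per patient (about 80 implants in 40 patients), for example a log-rank test that permutes HIV status over patients.
- Limit any year-1 success figure shown in December 2011 to implants followed for 1 year (those whose 1-year visit has fallen due, failures included), or use the same life table.

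In Study period, state the last placement date and reconcile it with the 3-year visit and the December 2014 end.

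The cost is wording and slightly more analysis work, with no new data. The method relies on censoring being unrelated to failure, so it does not cure loss that is related to failure. With about 5 expected failures the estimates will have little precision.

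### HIV group coincides with recruitment source, and no adjustment for starting bone is specified for the ANOVA of quantitative data

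*Combined protocol and SAP*

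**What the plan says.** All places are in the combined protocol and SAP.

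- **Source of the groups** (Study centre(s) and number of subjects planned): "20 HIV (+) patients will be selected from the 1917 Dental Clinic and 20 patients will be selected from UAB School of Dentistry patients". Treatment is shared: "Total 40 patients will be treated in the 2nd floor main clinic". No matching or stratification is described.
- **Eligibility** (Target patient population): the controls are "20 HIV-negative patients following the same requirements as above". On starting bone the list has "Minimal available bone height 10mm", with no upper limit, together with "Misch Available Bone classification divisions A, B, C" and "Misch Bone Density classification D1, D2, D3". Sites in either arch are allowed. Past smokers can enter: "Non- smoker (quite smoking at least 6 months" is the limit.
- **Outcome** (Efficacy): the primary variable is implant success by the Albrektsson and Zarb criteria. Radiographic bone height of each implant is examined at each interval and is the only quantitative measure under that heading.
- **Baseline imaging** (Investigational product/comparator, item 1; Additional clinical assessments, item 1): a cone beam CT is taken before placement. It has no stated role in the analysis.
- **Analysis** (Statistical methods): "With rigorous inclusion/exclusion criteria proposed, parametric data will be analysed using ANOVA methods". No factor, covariate or handling of baseline is named. Yes/no criteria go to chi-square.

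**The concern.** HIV status cannot be randomised, and here it coincides completely with where the patient was recruited. The shared eligibility list bounds both groups but does not balance them within the bounds. Two groups can both satisfy a 10 mm minimum, divisions A to C and densities D1 to D3 and still differ in average starting bone. The plan nevertheless gives eligibility as its only support for ANOVA.

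If follow-up bone height depends on starting bone, a difference between the sources passes into the group comparison. It could be reported as an HIV effect on bone, or cancel a real one. The plan as written gives no way to tell these apart, although the pre-operative scan that would help is already scheduled.

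**Working it through.** The documents give no test level, effect size, SD or derivation of the 40 patients, so there is no planned figure to reproduce.

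**Inputs from the documents:** 20 v 20 patients; about 80 implants budgeted, so 80/40 = 2 per patient on average; a pre-operative CBCT for every patient.

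**Assumptions:** two-sided 5% test; one value per patient; outcome and starting bone each with SD 1 within group; gap in starting bone between sources g = 0.25 or 0.5 SD; correlation ρ between starting and follow-up height from 0 to 0.7.

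**Unadjusted test of bone height.** Bias = ρ × g. The standard error is √(2/20) = 0.316. The rejection rate comes from the noncentral t with 38 df and noncentrality ρg/0.316. For 80% power without a gap, the true effect must be 0.909 SD (0.909/0.316 = 2.875). With an opposing gap the noncentrality is (0.909 − ρg)/0.316.

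For g = 0.5:

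| ρ | bias (SD) | false-positive rate | power for the 0.909 SD effect, gap opposing |
|---|---|---|---|
| 0 | 0 | 5.0% | 80% |
| 0.1 | 0.05 | 5.3% | 75% |
| 0.3 | 0.15 | 7.5% | 65% |
| 0.5 | 0.25 | 12.0% | 53% |
| 0.7 | 0.35 | 19.0% | 41% |

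For g = 0.25 at ρ = 0.3 / 0.5 / 0.7, the false-positive rate is 5.6 / 6.7 / 8.4% and the masked power 73 / 68 / 62%.

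**Loss counted from pre-operative height.** Bias = (1 − ρ)g with SD √(2(1 − ρ)). For g = 0.5 at ρ = 0.3 / 0.5 / 0.7, the standardised bias is 0.35/1.183 = 0.296, 0.25/1 = 0.25 and 0.15/0.775 = 0.194. The test rejects 14.9 / 12.0 / 9.2% of the time. A change score does not by itself remove the problem.

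**ANCOVA on group and starting bone** (simulated, 20,000 trials per case, g = 0.5). The false-positive rate is about 5% throughout. Power for the 0.909 SD effect at ρ = 0 / 0.3 / 0.5 / 0.7 is about 76 / 80 / 87 / 96%.

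**Adding arch to that model.** Suppose arch has no effect on bone but its mix differs between groups. Power then falls to about 71 / 75 / 82 / 94% with a 65/35 mix and 62 / 66 / 75 / 88% with a 75/25 mix.

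**Unit of analysis.** Assume two implants per patient, ρ = 0.5 and within-patient correlation 0.3 / 0.5. ANCOVA treating 80 implants as independent rejects 8.3 / 11.4% under no effect; on patient means it rejects 4.7 / 5.2%. Hence one value per patient.

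**The case against.** **The plan does not rule out adjustment.** A reader might infer that the analysis is unadjusted by design. The text does not support that: ANOVA methods could include a factor such as arch. What stands is that none is specified and that eligibility is the only support offered. That ANOVA means bone height is also an inference, since the text speaks only of parametric data.

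**The harm rests on two undocumented inputs.** No gap between sources is reported, and nothing shows that follow-up height correlates with pre-operative height. If follow-up height is read relative to the implant, the two may share no reference point and the correlation could be near zero. The unadjusted test then keeps its 5.0%. This is fair and limits the claim to what could happen. All patients are also treated in one clinic under one eligibility list, which narrows some differences.

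**Arch.** A reader might treat arch as a confounder on the same footing. The documents show only that permanent restoration is set 3 months after placement in the mandible and 6 in the maxilla. At the 1-year visit that is 12 − 3 = 9 v 12 − 6 = 6 months since restoration, if on schedule. No effect of arch on bone is given, and the arch term costs power if the mix is unbalanced.

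**The primary outcome.** A reader might extend the point to implant success. One illustration is 97.5% v 90% success by arch, which averages 93.75% and matches the budgeted 5 failed of 80, though failure is not the same as missing the criteria. Chi-square on 20 v 20 then rejects 2.4% (65/35 mix) or 3.4% (75/25). With 95% v 80% it rejects 6.5% or 10.1%, but nothing in the documents supports those rates.

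**Starting bone may itself reflect HIV.** If the whole 0.5 SD gap is due to HIV, adjusting moves the estimate by 0.5ρ = 0.15 / 0.25 / 0.35 SD at ρ = 0.3 / 0.5 / 0.7. The two estimates then answer different questions, so both belong in the report.

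**Conclusion.** The point holds as a gap in prespecification that should be fixed, with medium confidence. Source and HIV status coincide, eligibility does not balance starting bone, and no adjustment is specified although the baseline measurement is already planned.

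The consequence concerns radiographic bone height. It ranges from nothing (5.0% false positives at zero correlation) to serious (19.0% at correlation 0.7 with a 0.5 SD gap, with power down to 41% if the gap opposes the effect). The gap and the correlation are both assumptions. The documents do not show that the sources actually differ, and the conclusion does not depend on the success outcome or on an arch effect.

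Adjustment removes only the part of a source difference carried by measured starting bone. Age, past smoking, density and unmeasured differences remain.

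**What to change.** In Statistical methods:

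1. For bone height at each visit, replace ANOVA by ANCOVA on one value per patient (the mean over that patient's implants). The terms are HIV group and pre-operative bone height at the site from the planning CBCT, averaged in the same way.
2. State the reference point of both heights, and whether loss is counted from the pre-operative height.
3. Name the baseline-adjusted estimate as primary and report the unadjusted one beside it, because starting bone may itself be affected by HIV.
4. Use arch only in a sensitivity analysis, for example as the share of the patient's implants in the maxilla.
5. Delete the opening clause about rigorous eligibility criteria as support for an unadjusted test.
6. Add a baseline table by group, and state that unmeasured differences between the sources remain.

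The cost is a few sentences and slightly more analysis, with no new data or visits. If starting bone is unrelated to the outcome and the gap is 0.5 SD, power is about 76% against 80% unadjusted. At correlation 0.5 with an opposing gap, it is about 87% against 53%.
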